Deep brain stimulation for severe obsessive compulsive disorder: Efficacy and mechanisms of ventral striatum and subthalamic nucleus targets

Protocol December 2012 version 1.1

1. Background

- 1.1. Obsessive compulsive disorder (OCD) has a lifetime prevalence of 1-2 % and is characterised by intrusive unwanted thoughts and compulsive behaviours that vary in intensity, frequency and character. The standard treatment is cognitive behaviour therapy (CBT) and/or serotonin re-uptake inhibitor (SRI) medication but these are ineffective in up to 40% of cases ¹. Symptoms in this treatment-refractory subgroup can be sufficiently severe that patients are unable to perform activities of daily living, sustain work or maintain relationships. The English NHS National Specialised Commissioning Group has commissioned services to provide assessment and intensive CBT and pharmacotherapy for such patients. Although these have good results ^{2, 3} there remains a truly refractory subgroup for whom ablation of the anterior cingulate cortex is an option ⁴. Prospective longitudinal studies of cingulotomy suggest a sustained 2-year response rate of 32% with few adverse events and a concomitant improvement in quality of life ^{5,6}.
- 1.2. Deep brain stimulation (DBS) may improve upon this success rate as the response can be modified following surgery - stimulation can be adjusted to optimise benefits and minimise adverse effects. DBS also has the advantage of reversibility in that stimulation can be switched off if the response is unsatisfactory and electrodes can be removed. Studies which have used similar response criteria to those of tissue ablation implicate two DBS brain targets as being particularly effective - the ventral striatum/ventral anterior capsule (VS/VC) and the subthalamic nucleus (STN). Two studies have found that 56% or 62% of patients respond with VS/VC electrodes stimulating ventral striatal grey matter and adjacent white matter fibres en route to and from medial and orbital frontal cortex ^{7,8}; a third study found 75% responded with STN electrodes stimulating the boundary between associative and limbic grey matter, although the criterion for success was less strict than that of the VS/VC studies ⁹. All three studies additionally found concomitant improvements in everyday function, suggesting that DBS can be considered a promising treatment for severe OCD.

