- 3.7.** OCD symptoms and cognitive impairment may be mediated by abnormal cortical excitability due to aberrant long term depression (LTD) synaptic plasticity¹⁸ and/or reduced GABA-mediated intracortical inhibition¹⁹. Transcranial magnetic stimulation (TMS) can be used to measure these neurophysiological processes safely in patients undergoing DBS and both abnormalities have been shown to normalise following DBS in other disorders²⁰. We will use TMS to assess these neural processes before and after DBS in OCD patients and test for whether there are differential changes from the two DBS sites and whether combined VS/VC and STN DBS produces more vigorous improvements compatible with our hypothesis concerning the superior clinical effects of this condition. We will measure intracortical inhibition not only at rest but also during the anticipation of reinforcement, previously shown to affect motor cortex excitability²¹ and which we predict will be specifically affected by VS/VC DBS.

4. Research Programme

- 4.1. Subjects:** Six patients will be recruited from the OCD National Specialist Commissioned Services of [name], South West London and St George's Mental Health Trust (SWLSG MHT) and [name], Herts Partnership NHS Foundation Trust (HPFT).
- 4.2. Inclusion criteria:** The inclusion criteria have been designed to be consistent with previous OCD DBS studies and to ensure that patients have not responded in a useful and sustained manner to either modifications of medication or any form of CBT⁴.

Patients must have undergone intensive treatment and have demonstrable treatment resistance as defined by:

- a. At least two SRIs for a minimum of 12 weeks at optimal British National Formulary (BNF) doses.
- b. Augmentation of SRI treatment with antipsychotic drugs administered at maximally tolerated doses or by extending the SSRI dose beyond BNF limits.
- c. Two trials of CBT of at least 10 hours.
- d. Failed inpatient treatment for OCD.

Patients must also satisfy the following criteria:

- e. Age > 20 years.

- f. Confirmation of a primary diagnosis of obsessive compulsive disorder (ICD10 F42.0—F42.9).
- g. Duration of illness of at least 10 years.
- h. At least 2 years of unremitting symptoms despite intensive psychopharmacological and psychological treatment or failure to sustain, over a 3 month period, a response to inpatient psychological treatment by at least 33% with accompanying optimised pharmacological therapy.

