6.4. DBS stimulus adjustment and blinding: Two neurologists making the DBS adjustments ([name] and [name]) will allocate 3 patients to receive STN DBS initially and 3 to VC/VS DBS. All other team members and the patient will be blind to the allocation. Each electrode has 4 electrical contacts at its distal tip (with a 0.5mm separation) to allow fine tuning of the exact site for stimulation delivery. The optimal DBS parameters will be derived in an iterative fashion over a period lasting up to 2 weeks at the start of each 12 week stimulation block. This will require the patient to visit the DBS unit on a daily basis. At the outset, each contact will be screened with voltages up to 4V (STN electrodes) or 8V (VC/VS electrodes) using monopolar stimulation and a pulse width of 60us, and frequency of 130Hz. Note will be made of the immediate clinical effects from stimulation delivered through each contact in turn, and the threshold associated with positive and negative effects. Expected acute adverse effects of stimulation include transient sadness, anxiety, euphoria, giddiness or hypomania ^{7, 9}. These will be monitored and documented with the use of visual analogue rating scales which rate subjective feelings ²⁴. Stimulation will be adjusted to avoid any sustained negative physical or psychiatric symptoms. In the absence of any acute clinical effects, the post-operative imaging will be used to select the contact closest to the planned target. The initial optimal stimulation parameters will be refined according to patient feedback as often as necessary over the first 2 weeks, including possible use of stimulation through multiple contacts per electrode or using a bipolar configuration. These parameters will then be kept constant through the remainder of each 12 week block with further adjustment performed only in the event of delayed physical or psychiatric adverse events, considered by the trial team to be directly attributable to the stimulation.

6.5. Clinical assessments: OCD and co-morbid disorders will be assessed using The Mini International Neuropsychiatric Inventory (MINI) ²⁶ as part of the assessment of inclusion/exclusion criteria. In addition, Young Schema Questionnaire (YSQ) ⁴⁹ will be used to identify comorbid Personality Traits. Regular clinical assessments of the strength and

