6.7. TMS assessments

During TMS electromyography recordings will be made from abductor pollicis brevis (APB) and first dorsal interosseus (FDI) muscle using surface electrodes. Signals will be amplified and band pass filtered at a sample rate of 5000 Hz. TMS will be applied using a 70 mm figure of eight coil and Magstim 200 generators.

- a. **Cortical plasticity assessment:**
Paired associative stimulation (PAS) after localisation of the “hotspot” the resting (RMT) and active (AMT) motor thresholds will be determined. At 0.5, 15 and 30 min after PAS, we will obtain a stimulus response curve; MEPs will be recorded at each intensity from RMT-10% maximum stimulator output to RMT+30%. The inhibitory PAS10 paradigm (200 pairs, at 0.25 Hz) will be used. Median nerve stimulation (constant current generator) at 3x perceptual threshold intensity (duration 0.2 ms) will be delivered before TMS over the APB “hotspot” (intensity at 1 mV MEP prior to the start of the procedure).
- b. **Intracortical inhibition (SICI) assessment:**
TMS will be delivered to the FDI “hotspot”. The first, conditioning-stimulus, will be set at 80% AMT and the second, test stimulus at a 1 mV MEP level when given alone. Interstimulus intervals of ^{2,3} will be explored (n=12 per interval, randomly intermixed). SICI will be calculated by pooling 2 and 3 ms data and expressed as the ratio between conditioned and unconditioned trials. SICI will also be combined with a reward paradigm ²¹.

6.8. Timing of assessments and procedures: *(Please also see Table 1)* All assessment will be performed prior to surgery. Cognitive and TMS assessments will be performed additionally at the end of each of the 3 DBS periods, at the end of the optimisation of DBS period and at the end of CBT. Where possible, alternative forms of the tests will be used to avoid practice effects. Clinician-based clinical assessments will additionally take place monthly or more often if judged necessary. Patient self-report assessments will additionally take place at the end of each of the 3 DBS periods, at the end of the optimisation of DBS period and at the end of CBT.

7. Data Analysis

7.1. Descriptive analysis will be used to quantify changes in clinician-related YBOCS scores by using visual plots and specifying means and 95% CIs or medians and IQRs. We will then compare these changes using Friedman's ANOVA to account for the lack of independence between observations.

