7.2. The primary efficacy measure will be the clinician-rated YBOCS total scores. Friedman's ANOVA across all 4 conditions (pre-op baseline and after 3 months DBS in STN, VC/VS and STN+VC/VS) will be performed. A categorical efficacy measure, responder/non-responder status after each 3 month DBS block will be defined as $\geq 35\%$ decrease in YBOCS and will be analysed with the McNemar exact test for comparison of the VC/VS and STN DBS conditions. Descriptive analysis in addition to Friedman's ANOVA will also be used to analyse the mechanistic hypotheses on the following variables: MADRS, SSRT, ID/ED, probabilistic reversal learning, affective go/no go scores and TMS. The additional benefit of CBT will be analysed using Wilcoxon matched-pairs before and after CBT.

7.3. These data will also allow an estimate of mean effect and variance of the main effect to be made to allow a sample size calculation for a future fully powered trial.

8. Ethics and patient safety

8.1. Clinical care: All patients will be under the care of NHS OCD specialised services and their local community mental health team (CMHT). Consistent with the existing nationally commissioned clinical pathway, all potential participants will be offered the choice of anterior cingulotomy or DBS. Although this study is designed to examine the effect of DBS and not to compare the two procedures, adopting the standard care pathway will ensure that existing robust governance and consent procedures will be applied for all participants.

8.2. Monitoring for potential DBS adverse effects: The published risks of STN and VC/VS stimulation are mainly hypomania and anxiety, which are voltage dependent and 8, 9 and either self-limiting or resolved by modifying the stimulation settings. Clinical worsening, including lowering of mood has also been reported after stimulation is switched off. To

monitor and manage any adverse effects, the following procedures will be in place for each patient:

- a. Prior to surgery, in conjunction with the responsible OCD clinician [name] the study research clinician will contact the CMHT, speak to the responsible consultant and key worker about the study and provide regular progress reports.
- b. Patients will remain in hospital following changes in DBS for at least 24 hours following the final stimulation adjustment.

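### The only named test that isolates STN from VC/VS, an exact McNemar test in six patients, has under 1% power at the cited response rates; an estimated YBOCS difference should carry the comparison

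*Protocol*

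**What the plan says.** - Sample size (section 4.1): "Six patients will be recruited from the OCD National Specialist Commissioned Services". Every patient is implanted at both targets and stimulated at each in turn.
- Order (section 6.4): the neurologists who adjust the stimulation "will allocate 3 patients to receive STN DBS initially and 3 to VC/VS DBS". Stimulation at both sites together always comes last (section 5.1).
- Primary measure (section 7.2): "The primary efficacy measure will be the clinician-rated YBOCS total scores", analysed by Friedman's ANOVA over four conditions: pre-operative baseline, STN, VC/VS and both sites.
- Responder measure (section 7.2): "A categorical efficacy measure, responder/non-responder status after each 3 month DBS block will be defined as" a fall in YBOCS of at least 35%, and it "will be analysed with the McNemar exact test for comparison of the VC/VS and STN DBS conditions".
- Description (section 7.1): changes in YBOCS are to be plotted and summarised by "specifying means and 95% CIs or medians and IQRs".
- Later trial (section 7.3): the data will also supply a mean effect and variance for the sample size of a fully powered study.
- Background rates (section 1.2): "56% or 62% of patients respond with VS/VC electrodes" in two studies, and 75% responded with STN electrodes in a third, whose success criterion the protocol describes as less strict.

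The protocol gives no alpha, sidedness, power or sample-size justification for any test.

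**The concern.** Section 2.1 makes the comparison of VC/VS and STN in the same patients the overarching aim, and section 5.2 says that the purpose is to find the best site or sites for UK practice. Of the tests named in 7.2, only the McNemar test sets one single site against the other. The Friedman test covers four conditions at once, including baseline, and could be significant simply because stimulation beats no stimulation.

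The McNemar test uses only patients who respond at one site and not at the other. Six patients leave very few such pairs, so a non-significant result is almost built in. A reader could then take it as evidence that the two targets do equally well. The test also yields no estimate of the kind that section 7.3 wants for planning a later trial.

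**Working it through.** The protocol states no power or p-value figure to reproduce, so the check starts from the design.

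**Inputs.** n = 6 pairs (4.1). Response rates of 0.56 or 0.62 for VS/VC and 0.75 for STN (1.2). Two-sided alpha of 0.05 is assumed; one-sided results follow.

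**Step 1: attainable p-values.** With m discordant pairs, k of them in the more frequent direction, exact McNemar is a binomial test with probability 1/2: two-sided p = 2 × P(X ≥ k | m, 1/2), capped at 1.

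| Discordant split | Two-sided p | One-sided p |
|---|---|---|
| 6–0 | 2 × (1/2)^6 = 0.031 | 0.016 |
| 5–1 | 0.219 | 0.109 |
| 5–0 | 2 × (1/2)^5 = 0.0625 | 0.031 |
| 4–0 | 0.125 | 0.0625 |

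Only 6–0 falls below 0.05 two-sided. With five evaluable patients the best possible split is 5–0, so the two-sided test cannot reject.

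**Step 2: chance of a 6–0 split.** Let b be the probability of responding at STN only, and a at VC/VS only. The chance of two-sided significance is b^6 + a^6.

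Under within-patient independence, b = 0.75 × (1 − pV) and a = pV × 0.25:

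- pV = 0.56: b = 0.330, a = 0.140; 0.330^6 + 0.140^6 = 0.00130, or 0.13%.
- pV = 0.62: b = 0.285, a = 0.155; 0.285^6 + 0.155^6 = 0.00055, or 0.05%.

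Under the greatest discordance that these rates allow (nobody fails at both sites), b = 1 − pV and a = 0.25:

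- pV = 0.56: 0.44^6 + 0.25^6 = 0.0073 + 0.0002 = 0.0075, or 0.75%.
- pV = 0.62: 0.38^6 + 0.25^6 = 0.0030 + 0.0002 = 0.0033, or 0.33%.

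**Step 3: one-sided test (STN better).** A 5–0 split now also suffices, so the chance is b^6 + 6 × b^5 × (1 − a − b). This gives 0.7% to 1.4% under independence and at most 3.8% under maximum discordance.

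**Step 4: what the YBOCS difference offers in the same six patients.** Let SD be the standard deviation of the paired difference, STN minus VC/VS. The standard error is SD/√6. With period adjustment and three patients per order, the variance is SD²/4 × (1/3 + 1/3) = SD²/6, so the standard error is the same with one degree of freedom fewer, and SD is then the value within order group.

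| Analysis | df | 95% CI half-width | Difference for 80% power |
|---|---|---|---|
| Unadjusted | 5 | 2.571/√6 = 1.05 SD | 1.43 SD |
| Adjusted for period | 4 | 2.776/√6 = 1.13 SD | 1.54 SD |

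The last column comes from the noncentral t distribution with noncentrality (difference/SD) × √6, two-sided 0.05.

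**The case against.** The best defence is that exact McNemar is a valid test for paired binary data. Its type I error here is at most 3.1%. It is applied to a secondary measure; the primary analysis uses YBOCS scores, with descriptive summaries and intervals in 7.1; and 7.3 leaves power to a later trial. Post-hoc contrasts and interpretive wording are often left to an analysis plan, which is not at hand. All of this stands and lowers the severity. It does not remove the point, because the protocol itself fixes the test and names no other that isolates the two sites.

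Four stronger readings are tempting, and the documents do not support them.

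- *The test is certain to be uninformative.* It is not. True rates as far apart as 90% and 10% would give 28% power under independence, and the paired responder table is useful description whatever the p-value.
- *Significance always needs all six patients.* That depends on two-sided 0.05, which is an assumption. One-sided, a 5–0 split is enough.
- *Most patients will respond at both sites and drop out of the test.* Under independence only 0.56 × 0.75 = 42% to 0.62 × 0.75 = 46.5% do. A majority would need positive within-patient dependence, which the protocol does not give.
- *The test goes wrong if patients respond only in the later block.* The 3:3 order would then give a 3–3 split and p = 1, but those data show no site difference. Counterbalancing has taken the period effect out of the contrast, as intended.

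Nor does the protocol say that a non-significant result would be read as equivalence. That is a risk of interpretation, not a stated plan.

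**Conclusion.** The point holds at moderate severity. As a two-sided test at 0.05, the planned comparison of responders can succeed only on a 6–0 split and not at all after one dropout. Its power is 0.05% to 0.13% under independence and at most 0.75% under any dependence compatible with the cited rates. A one-sided test raises that ceiling only to 3.8%.

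The power figures rest on background rates from different studies with different response criteria, whereas this trial applies one criterion at both sites; they are illustrative ranges and not the trial's own planning assumptions. The attainable p-values depend only on the number of pairs, and their reading against 0.05 on the assumed level and sidedness.

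**What to change.** Reword section 7.2 as follows.

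1. Make the within-patient difference in clinician-rated YBOCS total, STN minus VC/VS, with its 95% CI the head-to-head comparison of the two sites, and say whether it is adjusted for period.
2. Report responder status descriptively as the paired 2×2 table for STN and VC/VS, with an exact 95% CI for the paired difference. Any McNemar p-value is supplementary only.
3. State that a non-significant result will not be read as equivalence of the sites.

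This needs no new patients, visits or data, and it serves the estimation goal of 7.3. The cost is the rewording and a plain admission of imprecision: with six patients the YBOCS difference can show only a large effect. Period adjustment widens the interval further, by one degree of freedom.

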- 1.3. Before DBS for OCD can be introduced into routine clinical practice, further research is required to determine the optimum DBS brain target. It may also be possible to improve upon the degree of response to DBS by understanding more about the mechanisms of action at the two target sites - although two-thirds were considered responders in previous studies, the patients remained symptomatic, being reduced from the 'extreme/severe' to the 'moderate' category ⁷. Furthermore, although CBT will not have previously been effective in these patients, DBS may reduce symptoms enough to enable them to use CBT more effectively and, indeed, the combination may result in a better outcome than DBS alone. To address these questions we have brought together a network of specialist OCD clinicians, leading OCD cognitive neuroscientists and expert DBS clinicians to undertake the first UK study of DBS for severe, medically intractable OCD.

2. Aims and Hypothesis

2.1. The overarching aim is to compare the effects of VC/VS and STN DBS in the same patients. We will test the hypothesis, grounded in cognitive neuroscience, that DBS at both sites is better than either site alone for treating the symptom dimensions of OCD. Specifically, we will employ novel cognitive paradigms and neurophysiological measures of cortical synaptic function to test the hypothesis that VS/VC and STN DBS have different mechanisms of action and that alleviation of OCD symptoms is mediated by improvement in mood/anxiety with VS/VC DBS and by directly interrupting obsessions and compulsions with STN DBS. We will additionally determine whether adjunctive CBT enhances the response to DBS by providing the cognitive and behavioural skills to optimise symptom management and daily function.

3. Scientific Rationale

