manifest in thoughts and actions ¹². Denys and colleagues ⁸ proposed that VS/VC DBS influences OCD symptoms via its effect on anxiety and mood. Taking this further, we hypothesize that stimulation of ventral striatal neurones influences reinforcement learning and emotion processing thereby improving mood and reducing anxiety and resulting in a decrease in the intensity of obsessions and compulsions.

- 3.3.** STN DBS on the other hand may have a more direct effect on obsessions and compulsions. The limbic STN, like the ventral striatum, is in a unique position to influence behavioural outputs of cortico-striatal-thalamo-cortical circuitry. This is because the STN receives a direct projection from right inferior frontal cortex which acts as a 'hyperdirect pathway', activation of which overrides neural processing in the direct cortico-striato-pallido-thalamic pathway. This results in the inhibition of ongoing, planned acts and thoughts ¹³. We therefore hypothesise that, via this inhibitory mechanism, stimulation of STN neurones enables OCD patients to interrupt their repetitive thoughts and actions resulting in a decrease in obsessions and compulsions.
- 3.4.** Accordingly, DBS at both sites, because of different mechanisms of action, is predicted to be clinically more effective than stimulation of either site alone. It also follows that if there are two mechanisms mediating OCD improvement, this should be evident in different patterns of cognitive and neurophysiological effects following DBS. In the proposed study we will test these predictions clinically and experimentally by using paradigms designed to distinguish the two hypothetical mechanisms of action.

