intensity of obsessive and compulsive symptoms will be made on Visual Analogue Scale (VAS) by using appropriate behavioural challenges, which will be designed specifically for each patient. Urge to perform compulsions will be monitored and quantified using similar VAS at each assessment point. The effect of DBS on OCD, affective symptoms, social function and quality of life will be assessed with the following validated scales:

OCD symptoms:

- a. Yale-Brown Obsessive Compulsive Scale Symptoms checklist (YBOCS-I) ²²
- b. Yale-Brown Obsessive Compulsive Scale (Version-II) ⁴⁷

Affective symptoms:

- c. Montgomery Asberg Depression Rating Scale (MADRS) ²⁷
- d. Beck Depression Inventory – Version 2 (BDI-II) ²⁸
- e. Young Mania Scale (YMS) ²⁹
- f. Barrett Impulsiveness Scale (BIS) ³⁰

Comorbid Tics:

- g. Yale Global Tic Severity Scale (YGTSS) ⁴⁸

Anxiety:

- h. Hamilton Anxiety Scale (HAS) ³¹
- i. Beck Anxiety Inventory (BAI) ³²

Social Function:

- j. DSM IV General Assessment of Function scale (GAF)
- k. Sheehan Disability Scale (SDS) ³³
- l. Cognitive Assessment Instrument of Obsessions and Compulsions (CAIOC-13) ³⁴

Subjective wellbeing:

- m. SF-36 ³⁵ (quality of life scale)

6.6. Cognitive assessments:

Years spent in education will be noted for all patients before they undergo the tests for general cognitive function.

General cognitive function:

- a. The National Adult Reading Test ³⁶
- b. CANTAB Paired Associate Learning Task (PAL) ³⁷
- c. Verbal Fluency ³⁸

Reinforcement learning and emotional processing:

- d. The probabilistic learning and reversal task ³⁹
- e. CANTAB Affective Go/No Go ³⁶

f. **CANTAB Reward Sensitivity Test**

Executive control:

- g. CANTAB Stop Signal Reaction Time Task ³⁶
- h. CANTAB ID/ED Task ³⁶

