The rationale for using these tests is that both stop-signal inhibition and extra-dimensional set-shifting have been shown to be sensitive to OCD (as well as in their first degree relatives) ¹⁷. Performance in both tasks is mediated by circuits including the inferior frontal cortex and orbitofrontal cortex ^{10,40}. Our hypothesis predicts that the SSRT and ID/ED will be more sensitive to changes induced by STN DBS. Preliminary work indicates that OCD patients with high YBOCS scores may be impaired in probabilistic reinforcement learning (70/30%); the Affective Go/No Go tests attentional biases in mood states. Our hypothesis predicts that these two tests will be more sensitive to changes induced by VC/VS DBS. Paired associate learning has also been shown to be deficient in OCD ⁴¹, although the precise neural substrates for this deficit are not known. Mild word finding difficulty and forgetfulness have been reported following DBS in several disorders and will be assessed with verbal fluency and PAL. This battery of tests will take approximately 1 hour to administer.

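### The mechanistic hypotheses are STN-versus-VC/VS contrasts, but section 7.2 tests them only with an omnibus Friedman test and leaves anxiety off the list

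*Protocol*

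**What the plan says.** Section 2.1 of the protocol proposes that "alleviation of OCD symptoms is mediated by improvement in mood/anxiety with VS/VC DBS and by directly interrupting obsessions and compulsions with STN DBS". Section 3.4 draws the consequence that, if there are two mechanisms, "this should be evident in different patterns of cognitive and neurophysiological effects following DBS". Section 3.5 undertakes to measure mood and anxiety under VS/VC stimulation and relate them to reinforcement learning. Section 3.7 undertakes to test whether TMS measures change differently at the two sites.

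Section 6.6 gives directions for four tasks. For two it states: "Our hypothesis predicts that the SSRT and ID/ED will be more sensitive to changes induced by STN DBS". For probabilistic learning and the affective go/no-go task it predicts the reverse, with VC/VS the more influential site.

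Section 6.5 lists two anxiety scales, the clinician-rated Hamilton scale (HAS) and the self-rated Beck inventory (BAI).

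Section 7.2 then sets descriptive analysis in addition to Friedman's ANOVA "to analyse the mechanistic hypotheses on the following variables: MADRS, SSRT, ID/ED, probabilistic reversal learning, affective go/no go scores and TMS". HAS and BAI are not in that list. The one direct STN-versus-VC/VS test in section 7 is McNemar's exact test on YBOCS responder status.

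**The concern.** The stated test and the stated hypotheses do not match. The prediction is crossed: STN should do more on SSRT and ID/ED, and VC/VS more on probabilistic learning, affective go/no-go, mood and anxiety. A Friedman test on one variable asks only whether some condition differs from some other. It has no direction and does not isolate STN against VC/VS.

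The other conditions in the test also have fixed places in time. Pre-op is always the first assessment, and section 5.1 puts combined stimulation always last. Practice, time, or a benefit shared by both sites can therefore drive the result. Only the two single-site blocks are counterbalanced, and for these variables that comparison has no stated test.

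Mechanism is in the trial's title. A significant Friedman result could be reported as support for two mechanisms when it says nothing about them, and the anxiety part of the hypothesis has no place in the stated analysis.

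**Working it through.** **Inputs.** Section 4.1: "Six patients will be recruited from the OCD National Specialist Commissioned Services", so n = 6. Section 6.4: the neurologists "will allocate 3 patients to receive STN DBS initially and 3 to VC/VS DBS", and every patient then receives both sites, so the site contrast is within patient. Section 7.2 defines the Friedman test for YBOCS over k = 4 conditions: pre-op, STN, VC/VS and combined. It does not repeat the set for the mechanistic variables, so both k = 4 and k = 3 (DBS conditions only) are checked. The protocol gives no alpha, effect size or power for these variables, so there is no figure of its own to reproduce. A two-sided 0.05 is assumed below.

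**Formula.** With rank sums R_j, Q = 12 / [n k (k + 1)] × ΣR_j² − 3 n (k + 1).

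**Four conditions, no site difference.** Pre-op is worst in all six patients and the other ranks are balanced, so the rank sums are 6, 18, 18, 18.
- ΣR² = 36 + 3 × 324 = 1008.
- Q = (12/120) × 1008 − 90 = 100.8 − 90 = 10.8.
- Chi-square on 3 df gives p = 0.013; exact p = 0.006.

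This is the smallest Q possible once pre-op is worst in all six. If pre-op is second worst in one patient, the most balanced rank sums are 7, 17, 18, 18. Then ΣR² = 49 + 289 + 324 + 324 = 986 and Q = 98.6 − 90 = 8.6 (exact p = 0.029).

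**Three DBS conditions, no site difference.** Combined is best in all six and the two sites are balanced, so the rank sums are 18, 9, 9.
- ΣR² = 324 + 81 + 81 = 486.
- Q = (12/72) × 486 − 72 = 81 − 72 = 9.0.
- Chi-square on 2 df gives p = exp(−4.5) = 0.011.

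Dropping pre-op therefore does not remove the problem.

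**How often this would happen.** This was simulated with four conditions and normal errors, with effects in SDs of a within-patient difference (assumed values) and rejection at Q ≥ 7.6, which has size 0.043. All three DBS conditions differ from pre-op by the same amount, so the sites are identical.

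| Common shift from pre-op (SD) | Friedman rejects |
|---|---|
| 0.25 | 0.06 |
| 0.5 | 0.13 |
| 0.75 | 0.26 |
| 1 | 0.44 |
| 1.5 | 0.79 |
| 2 | 0.95 |

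If instead STN and combined each improve by 2 SD and VC/VS not at all, the test rejects with probability 0.99. At that effect size it barely separates a real site difference (0.99) from none (0.95).

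**The direct contrast.** With six paired differences, an exact two-sided Wilcoxon test reaches 0.05 only if all six have the same sign: p = 2/2⁶ = 2/64 = 0.031. When the sites are equal it rejects with probability 0.031, whatever the common effect. Its power is 0.35, 0.66 and 0.87 for a true site difference of 1, 1.5 and 2 SD.

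**The case against.** The strongest reply is that section 7.2 does not rely on the Friedman test alone. Descriptive analysis is planned for the same variables and will show STN beside VC/VS. With six patients, and data meant to size a later trial, that is much of the evidence. This stands: it would be wrong to say that the sites are never compared, and the gap is in the formal test. But section 3.7 promises a test of differential change, and the test named in 7.2 is not one.

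Practice is also partly handled. Section 6.8 uses alternative test forms where possible, and Stage 1b follows up to 20 non-DBS patients at the same intervals. Alternative forms limit practice without excluding it, Stage 1b has no stated role in section 7, and an equal real benefit of both sites gives the same signal.

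A reader might infer that practice would make every task significant. The documents do not support that. They give no size for a practice effect, the Q = 10.8 pattern is a worst case (about 1% of simulated trials at a 0.5 SD shift and 10% at 1 SD), and MADRS and TMS are not learned tasks. Nor does the protocol state that the four-condition set applies to these variables; that is only implied.

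Finally, pairwise contrasts are often left to a statistical analysis plan, and none is shown here. Silence alone would be no finding. The point rests on what 7.2 does fix: a test and a variable list that do not fit sections 2.1, 3.4, 3.5, 3.7 and 6.6.

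**Conclusion.** The point holds as a mismatch between hypothesis and stated analysis. A significant omnibus Friedman test on a mechanistic variable is not evidence that the two sites work differently. It can arise with no site difference at all, at p = 0.013 with four conditions or p = 0.011 with three. The omission of HAS and BAI is a plain inconsistency with sections 2.1 and 3.5.

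The two worked p-values need only n = 6 and the stated rank patterns. The rejection rates rest on assumed effect sizes, normal errors and a 0.05 level, none of which the protocol gives. A reader might take the word mediated in section 2.1 as a promise of a mediation model. It is the wording of a hypothesis, and its use there is not counted as a fault.

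**What to change.** In section 7.2:

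- State the within-patient STN minus VC/VS difference as the contrast of interest for each listed variable, including the TMS measures.
- Add HAS to the list, with BAI as support.
- Give the predicted direction from section 6.6 for the four cognitive tasks, and from sections 2.1 and 3.2 for mood and anxiety. Section 6.6 gives no direction for mood, anxiety or TMS.
- Report each contrast as an exploratory estimate with an interval, and show the individual differences by order group.
- State that a significant omnibus Friedman test is not evidence of different mechanisms.

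The cost is a few sentences and a little analysis, since all the measures and the counterbalancing are already planned. The downside is low resolution. The smallest two-sided paired Wilcoxon p is 0.031, which cannot meet 0.05/6 = 0.0083 if the six listed variables were adjusted for multiplicity. A formal period-adjusted rank test would be weaker still: three patients per order give 20 arrangements, so its smallest two-sided p is 2/20 = 0.10. That is why order is better displayed than tested. A composite score over six patients, or subtraction of the non-randomised Stage 1b group's change, is not needed.
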